3.3.4 Removal of patients from therapy or assessments

3.3.4.1 Removal of individual patients

A patient must be withdrawn from the trial if any of the following criteria apply:

- The patient withdraws consent (patients are free to discontinue their participation in this study at any time without the need to justify the decision).

In this event, the patient will be asked to have an end of treatment investigation and the data collected until the point in time when withdrawal occurred will be included in the final analysis of the trial data. No further follow-up will be performed if the patient does not agree to further visits however patients might be contacted to obtain information on patient's status.

A patient must be withdrawn from active treatment if any of the following apply:

- The patient requests discontinuation of active treatment but agrees to be followed-up
- The patient is no longer able to receive active treatment (e.g. due to adverse events, surgery, concomitant diagnoses, concomitant therapies or administrative reasons). The investigator may also stop a patient's treatment if the patient is no longer able to attend study visits e.g. due to worsening of disease
- Unacceptable toxicity occurs which does not recover to a degree that allows treatment continuation
- Further dose reductions are considered necessary but would not be permitted according to the protocol

Treatment may be stopped in an individual patient after discussion between the sponsor and the investigator if eligibility criteria are violated and/or the patient fails to comply with the protocol, e.g. no adherence to restrictions, non-attendance at study assessments.

The EOT information should be obtained. All patients who end active treatment (but not the trial) will be followed up as described in [section 6.2.3](#).

Patients who were withdrawn during the first treatment cycle with co-administration of itraconazole and volasertib or during second treatment cycle with volasertib will be replaced, whereas patients withdrawn at a later stage will not be replaced.

3.3.4.2 Discontinuation of the trial by the sponsor

Boehringer Ingelheim reserves the right to discontinue the trial overall or at a particular trial site at any time for the following reasons:

1. Failure to meet expected enrolment goals overall or at a particular trial site,
2. Emergence of any efficacy/safety information that could significantly affect continuation of the trial
3. Violation of GCP, the CTP, or the contract by a trial site or investigator, disturbing the appropriate conduct of the trial.

Proprietary confidential information.

© 2017 Boehringer Ingelheim International GmbH or one or more of its affiliated companies. All rights reserved.
This document may not - in full or in part - be passed on, reproduced, published or otherwise used without prior written permission.

4. Any other administrative reasons, including discontinuation of the clinical development program with volasertib

The investigator / the trial site will be reimbursed for reasonable expenses incurred in case of trial termination (except in case of the third reason).

3.3.5 Re-treatment criteria for repeated cycles

To continue treatment with further cycles, the following criteria must be met:

1. Clinical benefit after volasertib treatment based on investigator's assessment (clinical response, or absence of progression, or symptom improvement). In case of symptom improvement despite disease progression a repeated cycle may be allowed upon the agreement of the clinical monitor and the investigator
2. a) Neutrophils $\geq 1\ 500/\text{mm}^3$ and platelets $\geq 100\ 000/\text{mm}^3$
b) In case criterion 2a) is not fulfilled, the peripheral blood should be re-evaluated at weekly intervals. As soon as criterion 2a) is met, the treatment should be continued unless other criteria for discontinuation or withdrawal apply (see [section 3.3.4.1](#)).
3. Acceptable tolerability (according to the investigator judgment) and recovery from drug related AEs to CTCAE levels that allow further treatment
4. Unacceptable toxicities (according to [5.2.6](#)) are recovered to pre-treatment values or CTCAE Grade 1, whichever is higher

3.3.6 Handling of patients removed from active treatment/trial

All withdrawals will be documented and the reason for end of treatment recorded and discussed, as necessary, in the final report of the trial.

As soon as a patient is withdrawn from the trial, the next scheduled visit and the EOT should be performed if feasible. Every effort should be made to follow-up patients in case an AE is still ongoing at the time of withdrawal / at the EOT visit.

Patients who withdraw prior to first treatment will not be included in the analysis. They will be entered into the trial data base, the reason for withdrawal documented and reported descriptively and by patient listing in the final report of this trial.

Patients who do not complete the first two cycles will be replaced.

Proprietary confidential information.

© 2017 Boehringer Ingelheim International GmbH or one or more of its affiliated companies. All rights reserved.
This document may not - in full or in part - be passed on, reproduced, published or otherwise used without prior written permission.

4. TREATMENTS

4.1 TREATMENTS TO BE ADMINISTERED

Volasertib will be administered to the patients in two consecutive treatment cycles on day 1 of a 21 day treatment cycle. The first volasertib infusion will occur after pretreatment with itraconazole from Day-3 to Day 1. Itraconazole will be continued for another 14 days after volasertib administration. In the second cycle, volasertib will be administered without itraconazole.

Repeated treatment cycles (≥ 3) of volasertib monotherapy can be administered in patients for whom clinical benefit is obtained.

Volasertib doses will be calculated as free base of the chloride salt. 1.00 mg volasertib (free base) equals 1.18 mg volasertib chloride salt.

In case of unexpected toxicity due to concomitant medication of volasertib and itraconazole, a reduced dose of 250 mg or 200 mg may be administered to the patients.

4.1.1 Identity of BI investigational product and comparator product(s)

Substance:	volasertib
Pharmaceutical form:	Solution for infusion (to be diluted with saline 0.9% before administration)
Source:	Boehringer Ingelheim Pharma GmbH & Co. KG
Unit strength:	2 mg/mL (200 mg/ 100 mL vial or 350 mg / 175 mL vial)
Posology:	Infusion over 120 minutes
Route of administration:	intravenous
Daily dose:	300 mg
Duration of use:	Single dose on day 1 of a 3 week cycle

Perpetrator Drug:

Substance:	itraconazole (Orungal®)
Pharmaceutical form:	capsules
Source:	[REDACTED]
Unit strength:	100 mg / capsule
Posology:	daily 200 mg
Route of administration:	oral
Daily dose:	200 mg
Duration of use:	18 days (three days before administration of volasertib, continuing from Day 1 till Day 15)

Proprietary confidential information.

© 2017 Boehringer Ingelheim International GmbH or one or more of its affiliated companies. All rights reserved.
This document may not - in full or in part - be passed on, reproduced, published or otherwise used without prior written permission.

4.1.2 Method of assigning patients to treatment groups

This section is not applicable in this study.

4.1.3 Selection of doses in the trial

The data obtained from clinical studies performed to date does not indicate a deviation from dose-proportionality for volasertib within the dose ranges 12-125 mg and 200-450 mg when volasertib is administered as a constant intravenous infusion.

To meet the objectives of the study, the dose investigated was designed to cover the dose where clinical efficacy is anticipated. The selected dose for iv administration in the present study is the recommended phase II dose for solid tumour trials ([P11-14366](#)).

4.1.3.1 Potential dose reduction

Reduction of starting dose

Initially, patients will be treated sequentially. Single patients will be treated for the first cycle until three patients have completed the first cycle.

Thereafter, cohorts of 3 patients will be treated until the preliminary safety of volasertib in combination with itraconazole is confirmed.

If more than 1 out of 6 patients experiences unacceptable toxicity (DRT, Section 5.2.6) during the first treatment cycle, the dose of volasertib for subsequent patients will be deescalated to 250 mg in the first and second treatment period.

If more than 1 out of 6 patients treated at a volasertib dose of 250 mg experiences unacceptable toxicity during the first treatment cycle, the dose of volasertib for subsequent patients will be further deescalated to 200 mg in the first and second treatment period.

The highest dose for which the incidence of unacceptable toxicity is no more than 1 out of 6 will be used as the dose of volasertib for the first and second treatment cycle of all further patients included in the trial (MTD, cf. [Section 5.2.6](#)).

Dose reduction in individual patients

If a patient experiences unacceptable toxicity (DRT, Section 5.2.6) the patient can continue volasertib treatment at a lower dose if criteria for retreatment are met (see [Section 3.3.5](#)). Each occurrence of DRT will lead to a dose reduction by 50 mg of any subsequent volasertib infusion(s). No dose reduction of volasertib below 200 mg is allowed.

If a patient experiences a DRT at the 200 mg dose, i.e. a dose reduction to <200 mg would be required, the volasertib treatment will be permanently discontinued and the patient will move to the EoT visit.

Proprietary confidential information.

© 2017 Boehringer Ingelheim International GmbH or one or more of its affiliated companies. All rights reserved.
This document may not - in full or in part - be passed on, reproduced, published or otherwise used without prior written permission.

When a dose reduction of volasertib occurs, this applies to all subsequent cycles with no possibility to dose escalation back to the previous dose.

4.1.3.2 Dose escalation scheme

A patient who is eligible to continue therapy with volasertib beyond the 2nd cycle (see [Section 3.3.5](#)) may either be treated with the original dose or may receive a higher dose in the third and subsequent cycles. The dose can be increased by 50 mg after each cycle ≥ 2 up to a maximum dose of 350 mg in case of clinical benefit and good tolerability in the completed cycle (i.e., non-hematological drug related adverse events of less than CTCAE Grade 2 and / or hematological drug related adverse events of less than CTCAE Grade 3). Dose escalation will occur only upon agreement between investigator and sponsor. Patients should continue on the higher dose in all subsequent treatment cycles if well tolerated. The decision to escalate the dose can be made at the end of cycles ≥ 2 . No dose increases above 350 mg are allowed. After dose escalation to the 350 mg subsequent dose reductions are allowed as per [Section 4.1.3.1](#).

4.1.4 Drug assignment and administration of doses for each patient

4.1.4.1 First cycle (combined volasertib and itraconazole administration)

The treatment to be evaluated is as outlined in [Table 4.1.4.1: 1](#) below:

Proprietary confidential information.

© 2017 Boehringer Ingelheim International GmbH or one or more of its affiliated companies. All rights reserved.
This document may not - in full or in part - be passed on, reproduced, published or otherwise used without prior written permission.

Table 4.1.4.1: 1 Treatments to be administered in the first treatment cycle

Treatment	Substance	Formulation	Unit strength	To be reconstituted with	Total dose [mg]
oral	itraconazole	capsules	100 mg per capsule	N/A	3600 mg (18 times 200 mg)
iv	volasertib	solution for infusion	vial of 200 mg (calculated as free base) / 100 ml, 2 vials to be used or vial of 350 mg (calculated as free base) / 175 ml, 1 vial to be used	isotonic saline	300, potential dose reductions according to section 4.1.3.1

Itraconazole will be administered to the patients in 24 hour intervals, after meal, starting 72 hours before administration of the first intravenous infusion of volasertib and will continue to be given in 24 hour intervals up to Day 15 / 336 hours thereafter.

On day 1, volasertib will be administered to the patients as a two hour infusion between 8:00 and 10:00 h in the morning. The administration of the formulation will be performed under the supervision of the investigating physician or a designee. Cancer patients will receive an iv volasertib (dose according to [section 4.1.3.1](#)).

For preparation of the volasertib infusion solution, the preconcentrate of volasertib will be diluted in 0.9% physiological NaCl. For further details on the preparation of the infusion solution, please refer to the “Dilution and Handling of Clinical Trial Drug” document filed in the ISF.

4.1.4.2 Second cycle (volasertib without itraconazole administration)

The treatment to be evaluated is as outlined in [Table 4.1.4.2: 1](#) below:

Proprietary confidential information.

© 2017 Boehringer Ingelheim International GmbH or one or more of its affiliated companies. All rights reserved.
This document may not - in full or in part - be passed on, reproduced, published or otherwise used without prior written permission.

Table 4.1.4.2: 1

Treatments to be administered in the second treatment cycle

Treatment	Substance	Formulation	Unit strength	To be reconstituted with	Total dose [mg]
iv	volasertib	solution for infusion	vial of 200 mg (calculated as free base) /100 ml, 2 vials to be used or vial of 350 mg (calculated as free base) / 175 ml, 1 vial to be used	isotonic saline	300 potential dose reductions according to section 4.1.3.1

On day 1 of treatment cycle 2, volasertib will be administered to the patients as a two hour infusion between 8:00 and 10:00 h in the morning. The administration of the formulation will be performed under the supervision of the investigating physician or a designee. Cancer patients will receive an iv dose of 300 mg volasertib (calculated as free base) whereas dose reduction is possible.

The procedure for preparing the infusion solution is as described for treatment cycle 1.

4.1.4.3 Subsequent treatment cycles

Patients who are eligible for subsequent cycles (>2) of treatment with volasertib (for criteria to continue treatment see [section 3.3.5](#)) will receive volasertib as long as neither patient nor investigator requests treatment discontinuation. Volasertib will be administered as described for treatment cycle 1.

For possible dose reduction and dose escalation see [sections 4.1.3.1](#) and [4.1.3.2](#).

4.1.5 Blinding and procedures for unblinding

Not applicable. This trial will be performed according to an open-label design.

4.1.6 Packaging, labelling, and re-supply

For details of packaging and the description of the label, refer to the ISF.

Investigational product

Volasertib will be supplied in **100 and 175** mL vials containing 200 / 350 mg volasertib, respectively. Examples of the labelling of the medication will be found in the investigator site file (ISF). Volasertib will be labelled according to Annex 13 with trial number, medication number, name of product and strengths or identification code, pharmaceutical dosage form, quantity of dosage units, route and mode of administration, term 'clinical trial use' (domestic language), sponsor name and address, storage conditions, use-by date, investigator name.

Medication will be delivered to the investigators pharmacy where the total dose per patient will be prepared upon request from the investigator. For preparation of the volasertib infusion solution, the preconcentrate will be diluted in 0.9% sodium chloride. The content of more than one vial may be needed for the administration of the requested dose. For further details, please refer to the ISF.

Perpetrator

Itraconazole will be acquired as commercial product from the European market. According to Hungarian regulations, itraconazole will be regarded as IMP. Itraconazole primary packaging will be unchanged and will be re-labelled by Boehringer Ingelheim Pharma GmbH & Co. KG according to Annex 13 with trial number, medication number, name of product and strengths or identification code, pharmaceutical dosage form, quantity of dosage units, route and mode of administration, term 'clinical trial use' (domestic language), sponsor name and address, storage conditions, use-by date, investigator name and the term "Keep out of reach of children" (domestic language).

Please refer to [section 4.1.8](#) for drug accountability. All used, partially used and unused IMP will be destroyed at the site and will not be returned to the sponsor. Double signatures of study staff will be required for this on-site destruction.

4.1.7 Storage conditions

Volasertib solution for infusion as well as itraconazole will be stored in the hospital pharmacy in a limited access area at the temperature indicated on the trial drug label.

Proprietary confidential information.

© 2017 Boehringer Ingelheim International GmbH or one or more of its affiliated companies. All rights reserved.
This document may not - in full or in part - be passed on, reproduced, published or otherwise used without prior written permission.

4.1.8 Drug accountability

The investigator will receive the investigational drugs (volasertib and itraconazole) delivered by the sponsor when the following requirements are fulfilled:

- approval of the study protocol by the IRB / ethics committee,
- availability of a signed and dated clinical trial contract between the sponsor and the Head of Trial Centre,
- approval/notification of the regulatory authority, e.g. competent authority,
- availability of the curriculum vitae of the principal investigator,
- availability of a signed and dated clinical trial protocol or immediately imminent signing of the clinical trial protocol,

The investigator must maintain records of the product's delivery to the trial site, the inventory at the site, the use by each patient, and the return to the sponsor or alternative disposition of unused products.

These records will include dates, quantities, batch/serial numbers, expiry ('use by') dates, and the unique code numbers assigned to the investigational product(s) and trial patients. The investigator will maintain records that document adequately that the patients were provided the doses specified by the CTP and reconcile all investigational product(s) received from the sponsor. At the time of return to the appointed CRO, the investigator / pharmacist / investigational drug storage manager must verify that no remaining supplies are in the investigator's possession.

4.2 CONCOMITANT THERAPY, RESTRICTIONS, AND RESCUE TREATMENT

All concomitant therapies to provide adequate care may be given as clinically necessary (for restrictions see [4.2.2](#)). All concomitant therapies administered during the course of the study must be recorded in the eCRF. Trade name, indication, and dates of administration will be documented.

4.2.1 Rescue medication, emergency procedures, and additional treatment(s)

Rescue medication to reverse the action of volasertib is not available. Potential side effects of volasertib should be treated symptomatically. Symptomatic treatment of side effects or tumour-associated symptoms is allowed. During the first cycle, the use of growth factors such as granulocyte colony stimulating factor (G-CSF) for treatment of haematotoxicity is not encouraged except for life-threatening circumstances. After the first cycle, G-CSF is allowed at the discretion of the investigator and must be recorded in the eCRF.

Proprietary confidential information.

© 2017 Boehringer Ingelheim International GmbH or one or more of its affiliated companies. All rights reserved.
This document may not - in full or in part - be passed on, reproduced, published or otherwise used without prior written permission.

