5.2.6 Dose reducing volasertib toxicity

Dose reducing volasertib toxicity (DRT) (i.e. unacceptable volasertib toxicity) is defined as:

- Drug related CTCAE Grade 3 or greater non-haematological toxicity (except emesis or diarrhoea responding to supportive treatment; if drug related nausea, vomiting or diarrhea is sufficiently treated but nevertheless of grade ≥ 3 severity, this is considered),
or
- Drug related CTCAE Grade 4 neutropenia for more than 7 days
or
- Drug related CTCAE Grade 4 thrombocytopenia.

Patients who have experienced an unacceptable toxicity are eligible for re-treatment with volasertib at a reduced dose of volasertib as per [section 4.1.3.1](#).

The maximum tolerated dose of co-administration of itraconazole and volasertib (MTD) is defined as the highest dose for which the incidence of DRT is no more than 1 out of 6 patients.

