7.3.3 Safety analyses

All patients who receive at least one dose of study drug will be included in the safety evaluation. Safety analyses will be performed in accordance with BI standards.

Adverse events will be coded using the Medical Dictionary for Drug Regulatory Activities (MedDRA). Adverse events occurring prior to drug administration will be assigned to the screening period. Adverse events occurring within 21 days of most recent volasertib infusion will be considered to be on treatment.

Independent of this rule, the relationship of an adverse event to the study drug treatments will be assessed by the investigator. Adverse event information as reported in the eCRFs will be aggregated in a two step process. First, multiple recordings (AE occurrences) of the same adverse event will be combined into one AE episode (collapsing). The second step will combine all of the AE episodes of an adverse event into one AE record as needed for by-patient summaries (condensing).

Reporting of adverse events and laboratory data will follow the standard BI procedures. The analysis of adverse events will comprise various frequency tabulations. Tables will be produced for treatment cycle 1 (co-administration of volasertib and itraconazole), treatment cycle 2 (volasertib alone) and for all treatment cycles combined. DRTs and the MTD (see [Section 5.2.6](#)) will be reported.

Laboratory values will be listed, tabulated and compared with their reference ranges. They will also be assessed with regard to possible changes compared to baseline values and with regard to the comparison of the first and second treatment cycle. The frequency of possible clinically significant abnormalities will be tabulated.

Safety will also be assessed by evaluation of physical examination (see [Section 7.3.8](#)), vital signs (blood pressure, pulse rate) and 12-lead ECG. Change from screening and/or baseline as well as change between treatment cycle 1 and 2 will be compared descriptively.

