7.5 RANDOMISATION

This is a fixed sequence design; no randomization to a treatment or sequence is necessary.

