6. GENERAL ANALYSIS DEFINITIONS

6.1 TREATMENTS

In total, it was planned to include 24 patients in this two period trial with a fixed treatment sequence:

Treatment A: Day -3 to Day 15 of cycle 1: daily 200mg itraconazole

Day 1 of cycle 1: Single dose volasertib infusion 300mg

Treatment B: Day 1 of cycle 2 (Day 23 starting from Day 1 of cycle 1): Single dose volasertib infusion 300mg

For detail of dosage and formulation see section 4.1 in CTP. For detailed information on the handling of the treatment in the O*C views refer to Technical TSAP ADS plan

Time intervals for safety analysis are defined below. The analyses for safety endpoints will focus the on-treatment period of volasertib and contrast the safety profile within first cycle and second cycle during the study period. In addition, the safety endpoints will be summarized for the entire volasertib mono-therapy period.

Screening period: Screening to first dose of Itraconazole.

Itraconazole induction period: Start of first dose of Itraconazole to start of first dose of volasertib.

First cycle combo-therapy period: Start of first dose of volasertib to the start of the second cycle if patients received the second cycle mono-therapy, or to the 21 days after the first volasertib administration date if patients discontinued after the first cycle.

Second cycle mono-therapy period: Start of second dose of volasertib to the start of the cycle 3 if patients received cycle 3 mono therapy, or to the 21 days after second volasertib administration date if patients discontinued after the second cycle.

Mono-therapy period: Start of the second dose of volasertib to the last dose of volasertib plus 21 days.

Post-treatment period: After 21 days after last dose of volasertib.

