7.8.2 Laboratory tests

Special care must be taken to review the lab data because the data are entered manually at the sites. Any corrections will be documented.

Primary laboratory tests are defined as:

- Low values (-):calcium, creatinine clearance, haemoglobin, neutrophils, platelets, potassium, sodium, and total WBC
- High values (+): Alkaline Phosphatase, ALT, AST, CK, Creatinine, LDH, Total Bilirubin, troponin T, and uric acid

All other labs collected will be classified as secondary.

The following analyses will be presented for the primary laboratory tests:

- descriptive statistics for change from baseline (uses normalized values)
 - for the worst value during treatment, and
 - the last value during treatment
- frequency of patients with transitions in CTCAE grade from baseline to worst and last values during treatment (excludes Troponin I, uses standardized values), and
- frequency of patients with possible clinically significant abnormalities (uses standardized values).

For secondary parameters, the analyses will be restricted to:

- frequency of patients with possible clinically significant abnormalities.

GFR will be calculated from creatinine using the Cockcroft-Gault transformation. GFR will be calculated from normalized creatinine using Cockcroft-Gault. In this calculation, if normalized creatinine is less than the standard lower limit, then it was set equal to the limit.

All lab tables should be footnoted to indicate that values were excluded if they were collected more than 21 days after the stop of treatment.

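### The G-CSF rule loosens exactly when itraconazole stops, so the descriptive cycle 1 versus cycle 2 comparison of neutropenia could overstate the effect of itraconazole, and the SAP has no analysis to show by how much

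*Protocol*

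**What the plan says.** **G-CSF rule.** Protocol 4.2.1 says that in the first cycle the use of growth factors such as G-CSF "for treatment of haematotoxicity is not encouraged except for life-threatening circumstances". It continues: "After the first cycle, G-CSF is allowed at the discretion of the investigator and must be recorded in the eCRF".

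**Sequence.** Protocol 7.5: "This is a fixed sequence design; no randomization to a treatment or sequence is necessary". Cycle 1 is always the combination and cycle 2 always volasertib alone.

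**Comparison.** Protocol 7.3.3 tabulates adverse events by cycle and assesses laboratory values "with regard to the comparison of the first and second treatment cycle". SAP 6.1 says the safety analyses will "contrast the safety profile within first cycle and second cycle during the study period". SAP 7.8.1 tabulates adverse events, with CTCAE grade, within each period. SAP 7.8.2 names the primary laboratory tests: "Low values (-):calcium, creatinine clearance, haemoglobin, neutrophils, platelets, potassium, sodium, and total WBC". For these it plans change from baseline and CTCAE transitions to the worst and last value.

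**Handling of G-CSF.** Protocol 4.2 has every concomitant therapy recorded with indication and dates. SAP 7.2 provides general frequency tables and listings of medications. Neither these sections nor the protocol-violation categories in SAP 6.2 contain a by-cycle G-CSF table, a sensitivity analysis or any other rule for it.

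**The concern.** G-CSF acts directly on neutrophils, WBC and neutropenia, and the rule for its use changes at the boundary between test and reference treatment. Patients with bad counts in cycle 1 are plausible candidates for G-CSF in cycle 2, so its use may be selective as well as unequal. Lower neutropenia in cycle 2 could then come from stopping itraconazole, from G-CSF, or from both, and the planned tables would not tell them apart.

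Protocol 1.2 and 2.3 name suppression of haematopoiesis as the main toxicity. It is where a reader would look for the clinical consequence of an interaction. Safety and tolerability are secondary objectives (Protocol 2.2).

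**Working it through.** There is no figure in the plan to reproduce. Protocol 7.6 gives 24 evaluable patients without a power calculation, and neither document gives a neutropenia rate or a G-CSF rate. All risks below are therefore assumptions.

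**1. Direction and range if itraconazole has no effect.** Let p be the true neutropenia risk in either cycle, u1 and u2 the shares of at-risk patients given G-CSF in cycles 1 and 2 early enough to matter, and r the relative reduction in risk from G-CSF.

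- Observed cycle 1 risk = p(1 − u1·r)
- Observed cycle 2 risk = p(1 − u2·r)
- False difference = p·r·(u2 − u1)

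With u1 = 0:

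| p | u2 | r | Cycle 1 | Cycle 2 | Difference (points) | Ratio | Expected cases of 24 |
|---|---|---|---|---|---|---|---|
| 20% | 10% | 30% | 20.0% | 19.4% | 0.6 | 1.03 | 4.8 vs 4.7 |
| 35% | 30% | 50% | 35.0% | 29.8% | 5.3 | 1.18 | 8.4 vs 7.1 |
| 50% | 50% | 50% | 50.0% | 37.5% | 12.5 | 1.33 | 12.0 vs 9.0 |

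In the middle row, 5% or 10% G-CSF use in cycle 1 lowers the difference to 0.35 × 0.5 × 0.25 = 4.4 points or 0.35 × 0.5 × 0.20 = 3.5 points. The sign follows u2 − u1. If use is equal in the two cycles, the G-CSF component is zero.

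**2. Selective use, near a worst case.** Take 20 patients treated in both cycles, with a true risk of 40% in each. The eight affected in cycle 1 have an untreated cycle 2 risk of 70% and the other twelve 20%: (8 × 0.7 + 12 × 0.2)/20 = 40%. Suppose all eight get early G-CSF in cycle 2 and nobody gets it in cycle 1.

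- As observed, with G-CSF relative risk 0.7, 0.5 or 0.3: (5.6 × RR + 2.4)/20 = 31.6%, 26.0% or 20.4%. The false excess in cycle 1 is 8.4 to 19.6 points.
- Composite of neutropenia or G-CSF given: (8 + 2.4)/20 = 52% in cycle 2, and 40% in cycle 1.

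The as-observed rate and the composite bracket the true 40%. The as-observed difference (+8.4 to +19.6 points) and the composite difference (−12 points) bracket the true zero.

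**3. Cutting counts at the first G-CSF dose.** In the same example the eight high-risk patients lose their cycle 2 nadir. If they are dropped, the cycle 2 rate is 2.4/12 = 20%. If they are kept as non-events, it is 2.4/20 = 12%. The false difference becomes 20 to 28 points, larger than with no adjustment.

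**The case against.** A reader might infer that G-CSF is all but banned in cycle 1 and freely given in cycle 2, so that the comparison is biased and the trial will overstate the harm of itraconazole. The documents do not support that much.

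- **Wording.** Cycle 1 use is discouraged, with an exception; it is not prohibited. Later use is left to the investigator's judgement. Preventive use is not mentioned, although nothing excludes it.
- **Which outcomes move.** G-CSF started after neutropenia appears mainly changes its duration and the last value. Worst grade and incidence move only with early or preventive use.
- **Other differences between cycles.** A dose reducing toxicity lowers later doses by 50 mg (Protocol 4.1.3.1). Re-treatment requires recovered counts (Protocol 3.3.5). Two of the first three patients stopped after cycle 1 (SAP 7.4). These also tend to favour cycle 2, while cumulative myelosuppression could work against it. The net bias is unknown.
- **Stakes.** The comparison is descriptive, and the plan announces no test or claim about neutropenia. In the example of 20 patients, the standard error of the paired difference is about √(0.24/20) = 11 points, where 0.24 = 0.4 × 0.3 + 0.6 × 0.2 is the discordant share. That is as large as much of the possible bias.
- **Cycle 1 toxicity rule.** The rule for lowering the starting dose uses cycle 1 only, so cycle 2 G-CSF does not distort it. Keeping cycle 1 largely free of G-CSF is consistent with that purpose.

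All of this stands, and it limits the point to a possible distortion of unknown size. It does not remove the point: a descriptive contrast can still mislead, and the general medication tables do not show G-CSF by cycle or connect it to the neutropenia results.

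**Conclusion.** The concern holds in a limited form. The G-CSF rule is fully confounded with treatment, the affected comparison is planned, and the SAP has no rule for it. Whenever effective G-CSF use is higher in cycle 2, this component points toward an excess of neutropenia with itraconazole. Its size rests on assumption: 0.6 to 12.5 percentage points for a true risk of 20–50%, cycle 2 uptake of 10–50%, a 30–50% effect and no cycle 1 use. Values near 20 points need every affected patient to receive early G-CSF with a strong effect, and should not be read as an estimate.

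Whether the whole comparison is biased, and in which direction, cannot be told from the documents. The primary AUC and Cmax analyses are outside this point. It is a worthwhile SAP improvement and does not invalidate the trial.

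**What to change.** In SAP 7.8.1 and 7.8.2, leaving the clinical G-CSF rule as it is:

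1. Tabulate G-CSF use by cycle, with its start relative to the volasertib infusion and its indication.
2. For patients treated in both cycles, show by cycle the as-observed rate of Grade 3 or higher neutropenia and, beside it, the composite of Grade 3 or higher neutropenia or G-CSF given, labelled as a bounding sensitivity analysis.
3. Base any statement of excess neutropenia with itraconazole on both. If they disagree in direction, say that the data do not settle it.
4. Flag any cycle 1 G-CSF use where dose reducing toxicities are reported (Protocol 7.3.3). The neutropenia criterion in Protocol 5.2.6, "Drug related CTCAE Grade 4 neutropenia for more than 7 days", depends on duration, which G-CSF can shorten.
5. Do not cut neutrophil and WBC values at the first G-CSF dose. That censoring is informative and, as shown above, can enlarge the bias.

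The cost is SAP wording and a few extra tables from data already collected. The composite counts preventive G-CSF as an event, so it is only a bound and must not be reported alone. None of this corrects for the other differences between cycles, which should be stated as limitations of the comparison.
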